9.3 Clinical Study Report and Publications

A Signatory Investigator must be selected to sign the clinical study report.

For this protocol, the Signatory Investigator will be selected as appropriate based on the following criteria:

- External Principal Investigator designated at protocol development
- National Coordinating Investigator
- Study Steering Committee chair or their designee
- Subject recruitment (eg, among the top quartile of enrollers)
- Involvement in trial design
- Regional representation (eg, among top quartile of enrollers from a specified region or country)
- Other criteria (as determined by the study team).

The data collected during this study are confidential and proprietary to BMS. Any publications or abstracts arising from this study must adhere to the publication requirements set forth in the clinical trial agreement (CTA) governing [Study site or Investigator] participation in the study. These requirements include, but are not limited to, submitting proposed publications to BMS at the earliest practicable time prior to submission or presentation and otherwise within the time period set forth in the CTA.

10 GLOSSARY OF TERMS

| Term | Definition |
|---------------------|--|
| Complete Abstinence | 
If one form of contraception is required, Complete Abstinence is defined as complete avoidance of heterosexual intercourse and is an acceptable form of contraception for all study drugs. Female subjects must continue to have pregnancy tests. Acceptable alternate methods of highly effective contraception must be discussed in the event that the subject chooses to forego complete abstinence.
 
If two forms of contraception is required, Complete abstinence is defined as complete avoidance of heterosexual intercourse and is an acceptable form of contraception for all study drugs. Subjects who choose complete abstinence are not required to use a second method of contraception, but female subjects must continue to have pregnancy tests. Acceptable alternate methods of highly effective contraception must be discussed in the event that the subject chooses to forego complete abstinence.
 
Expanded definition Complete abstinence as defined as complete avoidance of heterosexual intercourse is an acceptable form of contraception for all study drugs. This also means that abstinence is the preferred and usual lifestyle of the subject. This does not mean periodic abstinence (eg, calendar, ovulation, symptothermal, profession of abstinence for entry into a clinical trial, post-ovulation methods) and withdrawal, which are not acceptable methods of contraception. Subjects who choose complete abstinence are not required to use a second method of contraception, but female subjects must continue to have pregnancy tests. Acceptable alternate methods of highly effective contraception must be discussed in the event that the subject chooses to forego complete abstinence
 |

11 LIST OF ABBREVIATIONS

| Term | Definition |
|-------------|--|
| AE | adverse event |
| ALT | alanine aminotransferase |
| ANC | absolute neutrophil count |
| AST | aspartate aminotransferase |
| AT | aminotransaminases |
| BOR | best overall response |
| BMS | Bristol-Myers Squibb |
| BP | blood pressure |
| BUN | blood urea nitrogen |
| C | Celsius |
| Ca | calcium |
| CAV | cyclophosphamide, doxorubicin, vincristine |
| CBC | complete blood count |
| CFR | Code of Federal Regulations |
| CI | confidence interval |
| CMH | Cochran-Mantel-Haenszel |
| CNS | central nervous system |
| CR | complete response |
| CRF | Case Report Form, paper or electronic |
| CT | computed tomography |
| CTA | clinical trial agreement |
| DILI | drug-induced liver disease |
| DMC | data monitoring committee |
| DOR | duration of objective response |
| ECG | electrocardiogram |
| ECOG | Eastern Cooperative Oncology Group |
| EDC | electronic data capture |
| ED-SCLC | Extensive Stage Disease |
| eg | exempli gratia (for example) |

| Term | Definition |
|-------------|--|
| FDA | Food and Drug Administration |
| FFPE | formalin-fixed, paraffin-embedded |
| FSH | follicle stimulating hormone |
| GCP | Good Clinical Practice |
| HBsAg | hepatitis B surface antigen |
| HBV | hepatitis B virus |
| HCV | hepatitis C virus |
| HIV | Human Immunodeficiency Virus |
| HR | heart rate |
| HR | hazard ratio |
| HRQoL | health related quality of life |
| HRT | hormone replacement therapy |
| ICD | International Classification of Diseases |
| ICF | informed consent form |
| ICH | International Conference on Harmonisation |
| ie | id est (that is) |
| IEC | Independent Ethics Committee |
| IHC | immunohistochemistry |
| ILD | interstitial lung disease |
| IMP | investigational medicinal products |
| IND | Investigational New Drug Exemption |
| IRB | Institutional Review Board |
| ITIM | immunoreceptor tyrosine inhibitory motif |
| ITSM | immunoreceptro tyrosine-based switch motif |
| IU | International Unit |
| IUD | intrauterine device |
| IV | Intravenous(ly) |
| IVRS | interactive voice response system |
| K | potassium |
| KM | Kaplan-Meier |

| Term | Definition |
|-------------|---|
| LCSS | Lung Cancer Symptom Scale |
| LDH | lactate dehydrogenase |
| LD-SCLC | Limited Stage Disease |
| LVEF | Left ventricular ejection fraction |
| mAbs | monoclonal antibodies |
| MRI | magnetic resonance imaging |
| N | number of subjects or observations |
| Na | sodium |
| N/A | not applicable |
| NCCN | National Comprehensive Cancer Network |
| NCI CTCAE | National Cancer Institute Common Toxicity Criteria for Adverse Events |
| NIMP | non-investigational medicinal products |
| NSCLC | non-small cell lung cancer |
| ORR | objective response rate |
| OS | overall survival |
| PBMC | peripheral blood mononuclear cell |
| PD | progressive disease |
| PD-1 | Programmed death receptor-1 |
| PFS | progression free survival |
| PK | pharmacokinetics |
| PO | per os (by mouth route of administration) |
| Pop PK | Population PK |
| PR | partial response |
| Q2W | every 2 weeks |
| RCC | renal cell carcinoma |
| RECIST | Response Evaluation Criteria in Solid Tumors |
| SAE | serious adverse event |
| SCLC | small-cell lung cancer |
| SD | stable disease |
| SNP | single nucleotide polymorphism |

| Term | Definition |
|-------------|--|
| TAO | Trial Access Online, the BMS implementation of an EDC capability |
| TCR | T-cell receptor |
| TMB | Tumor mutational burden |
| TTR | time to response |
| ULN | upper limit of normal |
| VAS | visual analogue scale |
| WBC | white blood cell |
| WOCBP | women of childbearing potential |

APPENDIX 1 MANAGEMENT ALGORITHMS

These general guidelines constitute guidance to the Investigator and may be supplemented by discussions with the Medical Monitor representing the Sponsor. The guidance applies to all immuno-oncology agents and regimens.

A general principle is that differential diagnoses should be diligently evaluated according to standard medical practice. Non-inflammatory etiologies should be considered and appropriately treated.

Corticosteroids are a primary therapy for immuno-oncology drug-related adverse events. The oral equivalent of the recommended IV doses may be considered for ambulatory patients with low-grade toxicity. The lower bioavailability of oral corticosteroids should be taken into account when switching to the equivalent dose of oral corticosteroids.

[figure not shown]
Consultation with a medical or surgical specialist, especially prior to an invasive diagnostic or therapeutic procedure, is recommended.

The frequency and severity of the related adverse events covered by these algorithms will depend on the immuno-oncology agent or regimen being used.

Updated 05-Jul-2016

GI Adverse Event Management Algorithm

Rule out non-inflammatory causes. If non-inflammatory cause is identified, treat accordingly and continue I-O therapy. Opiates/narcotics may mask symptoms of perforation. Infliximab should not be used in cases of perforation or sepsis.

[figure not shown]

Patients on IV steroids may be switched to an equivalent dose of oral corticosteroids (e.g. prednisone) at start of tapering or earlier, once sustained clinical improvement is observed. Lower bioavailability of oral corticosteroids should be taken into account when switching to the equivalent dose of oral corticosteroids.

Updated 05-Jul-2016

Renal Adverse Event Management Algorithm

Rule out non-inflammatory causes. If non-inflammatory cause, treat accordingly and continue I-O therapy

[figure not shown]

Patients on IV steroids may be switched to an equivalent dose of oral corticosteroids (e.g. prednisone) at start of tapering or earlier, once sustained clinical improvement is observed. Lower bioavailability of oral corticosteroids should be taken into account when switching to the equivalent dose of oral corticosteroids.

Updated 05-Jul-2016

Pulmonary Adverse Event Management Algorithm

Rule out non-inflammatory causes. If non-inflammatory cause, treat accordingly and continue I-O therapy. Evaluate with imaging and pulmonary consultation.

[figure not shown]

Patients on IV steroids may be switched to an equivalent dose of oral corticosteroids (e.g. prednisone) at start of tapering or earlier, once sustained clinical improvement is observed. Lower bioavailability of oral corticosteroids should be taken into account when switching to the equivalent dose of oral corticosteroids.

Updated 05-Jul-2016

Hepatic Adverse Event Management Algorithm

Rule out non-inflammatory causes. If non-inflammatory cause, treat accordingly and continue I-O therapy. Consider imaging for obstruction.

Patients on IV steroids may be switched to an equivalent dose of oral corticosteroids (e.g. prednisone) at start of tapering or earlier, once sustained clinical improvement is observed. Lower bioavailability of oral corticosteroids should be taken into account when switching to the equivalent dose of oral corticosteroids.

[figure not shown]
*I-O therapy may be delayed rather than discontinued if AST/ALT ≤ 8 x ULN or T.bili ≤ 5 x ULN.

**The recommended starting dose for grade 4 hepatitis is 2 mg/kg/day methylprednisolone IV.

Updated 05-Jul-2016

Endocrinopathy Management Algorithm

Rule out non-inflammatory causes. If non-inflammatory cause, treat accordingly and continue I-O therapy. Consider visual field testing, endocrinology consultation, and imaging.

[figure not shown]

Patients on IV steroids may be switched to an equivalent dose of oral corticosteroids (e.g. prednisone) at start of tapering or earlier, once sustained clinical improvement is observed. Lower bioavailability of oral corticosteroids should be taken into account when switching to the equivalent dose of oral corticosteroids.

Updated 05-Jul-2016

Skin Adverse Event Management Algorithm

Rule out non-inflammatory causes. If non-inflammatory cause, treat accordingly and continue I-O therapy.

Patients on IV steroids may be switched to an equivalent dose of oral corticosteroids (e.g. prednisone) at start of tapering or earlier, once sustained clinical improvement is observed. Lower bioavailability of oral corticosteroids should be taken into account when switching to the equivalent dose of oral corticosteroids.

[figure not shown]
*Refer to NCI CTCAE v4 for term-specific grading criteria.

[^]If SJS/TEN is suspected, withhold I-O therapy and refer patient for specialized care for assessment and treatment. If SJS or TEN is diagnosed, permanently discontinue I-O therapy.

Updated 05-Jul-2016

Neurological Adverse Event Management Algorithm

Rule out non-inflammatory causes. If non-inflammatory cause, treat accordingly and continue I-O therapy.

Patients on IV steroids may be switched to an equivalent dose of oral corticosteroids (e.g. prednisone) at start of tapering or earlier, once sustained clinical improvement is observed. Lower bioavailability of oral corticosteroids should be taken into account when switching to the equivalent dose of oral corticosteroids.

Updated 05-Jul-2016

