4.5.2.1 Nivolumab

No dose modifications of nivolumab are allowed for the management of toxicities experienced by individual subjects.

Dose delay criteria apply for all drug-related AEs. Treatment delays up to 6 weeks (42 days) from the last dose are allowable.

Nivolumab administration should be delayed for the following:

- Grade 2 non-skin, drug-related adverse event, with the exception of fatigue
- Grade 2 drug-related creatinine, AST, ALT and/or Total Bilirubin abnormalities
- Grade 3 skin, drug-related adverse event
- Grade 3 drug-related laboratory abnormality, with the following exceptions:
 - Grade 3 lymphopenia or asymptomatic amylase or lipase does not require dose delay
 - Grade ≥ 3 AST, ALT, Total Bilirubin will require dose discontinuation (see [Section 4.5.3.1](#))
- Any adverse event, laboratory abnormality, or intercurrent illness which, in the judgment of the investigator, warrants delaying the dose of study medication.

Subjects who require delay of nivolumab should be re-evaluated weekly or more frequently if clinically indicated and resume nivolumab dosing when re-treatment criteria are met

Criteria to Resume Treatment

Subjects may resume treatment with nivolumab when the drug-related AE(s) resolve to Grade ≤ 1 or baseline value, with the following exceptions:

- Subjects may resume treatment in the presence of Grade 2 fatigue
- Subjects who have not experienced a Grade 3 drug-related skin AE may resume treatment in the presence of Grade 2 skin toxicity
- For subjects with Grade 2 AST, ALT and/or Total Bilirubin Abnormalities, dosing may resume when laboratory values return to baseline and management with corticosteroids, if needed, is complete.
- Subjects with combined Grade 2 AST/ALT AND total bilirubin values meeting discontinuation parameters (Section 4.5.3.1) should have treatment permanently discontinued
- Drug-related pulmonary toxicity, diarrhea or colitis must have resolved to baseline before treatment is resumed. Subjects with persistent Grade 1 pneumonitis after completion of a steroid taper over at least 1 month may be eligible for retreatment if discussed with and approved by BMS Medical Monitor.
- Subjects with drug-related endocrinopathies adequately controlled with only physiologic hormone replacement may resume treatment after consultation with the BMS Medical Monitor. Adrenal insufficiency requires discontinuation regardless of control with hormone replacement

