4.5.3 Discontinuation Criteria

4.5.3.1 Nivolumab

Treatment with nivolumab should be permanently discontinued for the following:

- Grade 2 drug-related uveitis, eye pain or blurred vision that does not respond to topical therapy and does not improve to Grade 1 severity within the re-treatment period OR requires systemic treatment
- Grade 3 non-skin, drug-related adverse event lasting > 7 days or recurs, with the following exceptions for laboratory abnormalities, drug related uveitis, pneumonitis, bronchospasm, neurologic toxicity, hypersensitivity reactions, infusion reactions and endocrinopathies:
 - Grade 3 drug-related uveitis, pneumonitis, bronchospasm, neurologic toxicity, myocarditis, hypersensitivity reaction, or infusion reaction of any duration require discontinuation
 - Grade 3 drug-related endocrinopathies adequately controlled with only physiologic hormone replacement do not require discontinuation; Adrenal insufficiency requires discontinuation regardless of control with hormone replacement.
 - Grade 3 drug-related laboratory abnormalities do not require treatment discontinuation except:
 - ◆ Grade 3 drug-related thrombocytopenia > 7 days or associated with bleeding requires discontinuation
 - ◆ Grade ≥ 3 drug-related AST, ALT or Total Bilirubin requires discontinuation*
 - ◆ Concurrent AST or ALT > 3 x ULN and total bilirubin > 2x ULN
- * In most cases of Grade 3 AST or ALT elevation, study drug(s) will be permanently discontinued. If the investigator determines a possible favorable benefit/risk ratio that warrants continuation of study drug(s), a discussion between the investigator and the BMS Medical Monitor/designee must occur
- Any Grade 4 drug-related adverse event or laboratory abnormality (including but not limited to creatinine, AST, ALT, or Total Bilirubin) except for the following events which do not require discontinuation:
 - Grade 4 neutropenia ≤ 7 days
 - Grade 4 lymphopenia or leukopenia or asymptomatic amylase or lipase
 - Isolated Grade 4 electrolyte imbalances/abnormalities that are not associated with clinical sequelae and are corrected with supplementation/appropriate management within 72 hours of their onset
 - Grade 4 drug-related endocrinopathy adverse events, such as hyper- or hypothyroidism, or glucose intolerance, which resolve or are adequately controlled with physiologic hormone replacement (corticosteroids, thyroid hormones) or glucose-controlling agents,

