6.6 Potential Drug Induced Liver Injury (DILI)

Wherever possible, timely confirmation of initial liver-related laboratory abnormalities should occur prior to the reporting of a potential DILI event. All occurrences of potential DILIs, meeting the defined criteria, must be reported as SAEs (see [Section 6.1.1](#) for reporting details).

Potential drug induced liver injury is defined when all three of the following are present:

- 1) Aminotransaminase (AT, ALT or AST) elevation > 3 times upper limit of normal (ULN)
- 2) Total bilirubin > 2 times ULN, without initial findings of cholestasis (elevated serum alkaline phosphatase),
- 3) No other immediately apparent possible causes of AT elevation and hyperbilirubinemia, including, but not limited to, viral hepatitis, pre-existing chronic or acute liver disease, or the administration of other drug(s) known to be hepatotoxic.

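### The hepatic algorithm footnote in Appendix 1 permits delaying nivolumab at liver values for which Sections 4.5.3.1 and 4.5.2.1 require permanent discontinuation

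*Protocol*

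**What the plan says.** Four places in the protocol bear on the same patient.

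- **Section 4.5.3.1** opens with "Treatment with nivolumab should be permanently discontinued for the following". Among the laboratory criteria are "Grade ≥ 3 drug-related AST, ALT or Total Bilirubin requires discontinuation" and, as a separate item, "Concurrent AST or ALT > 3 x ULN and total bilirubin > 2x ULN". An asterisk on the first item leads to a note beginning "In most cases of Grade 3 AST or ALT elevation, study drug(s) will be permanently discontinued", which allows continuation to be discussed with the medical monitor. The concurrent item carries no asterisk.
- **Section 4.5.2.1**, under the criteria for resuming treatment, says "Subjects with combined Grade 2 AST/ALT AND total bilirubin values meeting discontinuation parameters (Section 4.5.3.1) should have treatment permanently discontinued".
- **Section 3.5** places the Section 4.5.3 criteria among the reasons for which a subject must stop investigational product.
- **Appendix 1**, in the footnote to the hepatic algorithm, says "I-O therapy may be delayed rather than discontinued if AST/ALT ≤ 8 x ULN or T.bili ≤ 5 x ULN". The footnote does not mention concurrent elevation and does not refer back to Section 4.5.3.1.

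On the standing of these texts, Section 4.5.1 says that treatment modifications follow the criteria in Sections 4.5.2 and 4.5.3. Section 4.5.1.1 says the algorithms were developed to help investigators manage adverse events, including hepatic ones, counts nivolumab as an agent they cover, and points to Appendix 1. The appendix describes itself as general guidance for all immuno-oncology agents.

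**The concern.** Both rules are written in multiples of ULN, so they can be compared without any toxicity-grade cut-off. The appendix offers delay as an alternative to discontinuation, and delay carries the prospect of restarting. For concurrent elevation the body excludes that alternative. An investigator facing an acute hepatic event is likely to open the hepatic algorithm. Someone who delays on the strength of its footnote would depart from Section 4.5.3.1 in good faith.

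What is at stake is patient safety and uniform handling across sites. The values concerned coincide with the two laboratory multiples in the potential drug-induced liver injury definition of Section 6.6.

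**Working it through.** No sample size, event count or error rate enters this point. The check compares two threshold regions. Let A be the higher of AST and ALT, and B total bilirubin, both in multiples of ULN. Cases are taken as drug-related, which is the scope of the laboratory criteria in Section 4.5.3.1.

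**Inputs**

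| Source | Action | Region |
|---|---|---|
| Section 4.5.3.1, concurrent item | Permanent discontinuation | A > 3 and B > 2 |
| Appendix 1, hepatic footnote | Delay permitted | A ≤ 8 or B ≤ 5 |

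**Step 1: does the concurrent item apply below Grade 3?** In the layout of Section 4.5.3.1 it sits in a sub-list about Grade 3 laboratory abnormalities, so one might confine it to that grade. Section 4.5.2.1 rules this out by applying the same parameters to combined Grade 2 values.

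**Step 2: narrow reading of the footnote.** Suppose both limits must hold, A ≤ 8 and B ≤ 5. The intersection with the discontinuation region is

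3 < A ≤ 8 and 2 < B ≤ 5.

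This is not empty. With A = 6 and B = 3: 6 > 3 and 3 > 2, so discontinuation is required; 6 ≤ 8 and 3 ≤ 5, so delay is permitted. A = 4 with B = 2.5 gives the same result. Reading the footnote parameter by parameter, with one limit for a transaminase rise and another for a bilirubin rise, leaves the same rectangle for a patient who has both.

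**Step 3: literal reading of the footnote.** With the word or taken at face value, the overlap is A > 3 and B > 2 with at least one of A ≤ 8 or B ≤ 5. This contains the rectangle and more. The size of the point does not rely on it.

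**Step 4: does the medical-monitor exception remove the overlap?** No. It is attached to the Grade ≥ 3 line and speaks only of Grade 3 AST or ALT elevation. It softens any conflict with the single-parameter rule, including the Section 4.5.2.1 line "AST, ALT, Total Bilirubin will require dose discontinuation", but does not reach the concurrent criterion.

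**Step 5: could the unseen figure remove it?** The box that carries the asterisk cannot be read in the text available, which is no fault of the plan. If the footnote belongs only to a more severe row, an overlap can still remain, for example at A = 6 and B = 4. A carve-out written inside the figure would remove it, and that possibility cannot be excluded.

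**The case against.** The strongest reply is that the protocol already indicates which text governs. Section 4.5.1 names Sections 4.5.2 and 4.5.3, not Appendix 1, as the basis for dose modifications. Section 3.5 makes the Section 4.5.3 criteria mandatory, and the appendix calls itself guidance. The concurrent rule is also repeated in the resume criteria, where a site should look before restarting. All of this stands and makes the body's precedence the natural inference. It remains an inference: Section 4.5.1.1 sends investigators to the algorithms without saying how they relate to Section 4.5.3.1, and there is no clause for conflicts.

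Four stronger readings are tempting, and the documents do not support them.

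- **That the two texts give opposite orders.** The footnote says therapy may be delayed; Section 4.5.3.1 directs discontinuation. Stopping satisfies both.
- **That any AST value qualifies for delay when bilirubin is at or below 5 x ULN.** That is one reading of an ambiguous conjunction, and it would also collide with the Grade 4 discontinuation rule in Section 4.5.3.1. The limits can equally be read one parameter at a time.
- **That these values amount to potential drug-induced liver injury.** Section 6.6 requires more: "Total bilirubin > 2 times ULN, without initial findings of cholestasis", and no other immediately apparent cause. It also governs reporting, not dosing. Only the two laboratory multiples coincide.
- **That hepatic discontinuation rates will differ by site.** This could happen, but nothing in the documents shows it or gives a frequency for concurrent elevation.

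**Conclusion.** The inconsistency is real. At least for drug-related AST/ALT above 3 and up to 8 x ULN together with bilirubin above 2 and up to 5 x ULN, the appendix footnote permits what Sections 4.5.3.1 and 4.5.2.1 forbid, and no passage expressly resolves it.

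The number of patients affected cannot be derived. The nearest figure is in Section 1.1.3.3: hepatic select adverse events in 4.5% of 268 nivolumab-treated melanoma subjects. If that rate carried over to roughly 280 subjects in Arm A (560 / 2), it would give 0.045 x 280 = 12.6, about 13 hepatic events of all kinds, of which concurrent elevation would be a subset. This is an assumption for scale only, since the population differs and the figure counts reported events rather than laboratory values.

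The conclusion rests on the footnote meaning what its visible words say. It does not touch the OS comparison, power or type I error. It merits correction because it concerns a stopping rule for safety, although the likely precedence of the body text limits its weight.

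**What to change.** Reconcile the hepatic footnote in Appendix 1 with Sections 4.5.3.1 and 4.5.2.1. Two forms of wording would do: a cross-reference from the footnote to Section 4.5.3.1 that says how concurrent elevation is handled, or an explicit statement of which text prevails where the algorithms and the dosing sections differ. The figure should be checked at the same time for the box that carries the asterisk, and the footnote's conjunction made unambiguous. Which clinical rule applies is for the clinical team to decide; none is proposed here.

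The cost is a small change of protocol wording or an administrative letter. No design element, analysis or data collection changes.

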4.5 Selection and Timing of Dose for Each Subject

4.5.1 Dosing Schedule

The dosing schedule is detailed below Table 4.5.1-1.

| Table 4.5.1-1: Dosing Schedule | | | | | | |
|---|------------------------|---------------|--------------------|------------------------|--------------------|---------------|
| | Week 1 | Week 2 | Week 3 | Week 4 | Week 5 | Week 6 |
| Arm A | | | | | | |
| Nivolumab 240 mg ^a q 2 weeks | Day 1 Nivolumab | | Day 1 Nivolumab | | Day 1 Nivolumab | |
| Arm B | | | | | | |
| Topotecan ^a IV 1.5 mg/m ² or capsule 2.3 mg/m ² or | Day 1 - 5 Topotecan | | | Day 1 - 5 Topotecan | | |
| Amrubicin ^a 40 mg/m ² | Day 1 - 3 Amrubicin | | | Day 1 - 3 Amrubicin | | |

^a Treatment continues until disease progression (or until discontinuation of study drug in subjects receiving nivolumab), discontinuation due to toxicity, withdrawal of consent, or the study ends.

All subjects will be monitored continuously for AEs while on study treatment. Treatment modifications (eg, dose delay, reduction, or discontinuation) will be based on specific laboratory and AE criteria, as described in Sections 4.5.2 and 4.5.3.

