If the criteria to resume treatment are met, the subject should restart treatment at the next scheduled timepoint per protocol.

If treatment is delayed > 6 weeks (42 days) from the last dose, the subject must be permanently discontinued from study therapy, except as specified in Section 4.5.3.1.

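### Appendix 1 bars nivolumab for good after diagnosed SJS or TEN, but the dosing rules in Sections 4.5.2.1 and 4.5.3.1 omit this and let a resolved Grade 3 skin event restart

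*Protocol*

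**What the plan says.** A footnote to the skin algorithm in Protocol Appendix 1 gives two instructions. For suspected cases: "If SJS/TEN is suspected, withhold I-O therapy and refer patient for specialized care for assessment and treatment". For confirmed cases: "If SJS or TEN is diagnosed, permanently discontinue I-O therapy". Neither sentence states a grade. SJS and TEN are mentioned nowhere else in the protocol or SAP text available for review.

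Section 4.5.1 places the operative dosing rules elsewhere: "Treatment modifications (eg, dose delay, reduction, or discontinuation) will be based on specific laboratory and AE criteria, as described in Sections 4.5.2 and 4.5.3". Section 3.5, which lists the mandatory reasons for stopping, likewise refers to Section 4.5.3 for further reasons.

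The nivolumab rules in those sections treat skin events as follows:

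- Section 4.5.3.1 (permanent discontinuation) has a general Grade 3 rule that leaves skin out: "Grade 3 non-skin, drug-related adverse event lasting > 7 days or recurs".
- Section 4.5.2.1 (delay) includes "Grade 3 skin, drug-related adverse event".
- Section 4.5.2.1 (resumption) states "Subjects may resume treatment with nivolumab when the drug-related AE(s) resolve to Grade ≤ 1 or baseline value". Its list of exceptions does not mention SJS or TEN.
- Section 4.5.2.1 then adds: "If the criteria to resume treatment are met, the subject should restart treatment at the next scheduled timepoint per protocol".

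**The concern.** The sponsor has decided that a patient with diagnosed SJS or TEN should not receive the drug again. That decision appears only in an appendix footnote, and the appendix describes itself as guidance. The sections that investigators are told to use for delay and discontinuation omit it, and their restart rule points the other way. An investigator could follow Sections 4.5.2.1 and 4.5.3.1 to the letter and re-dose a patient whom the sponsor's own algorithm excludes. What is at stake is the safety of individual patients, not the validity of any analysis.

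**Working it through.** There is no plan figure to reproduce. The check sets the rules side by side, followed by two small counts.

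**Drug-related, diagnosed SJS/TEN, by grade**

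| Grade | Appendix 1 | Sections 4.5.2.1 and 4.5.3.1 | Agree? |
|---|---|---|---|
| 4 | Permanent stop | Permanent stop under the general Grade 4 rule | Yes |
| 3 | Permanent stop | Delay, then restart at Grade 1 or less or at baseline | No |
| Below 3 | Permanent stop | No listed delay or stop for skin; investigator judgment only | No |

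The below-4 rows assume that no other stop applies (see the routes below).

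**Suspected SJS/TEN.** Appendix 1 withholds treatment. Section 4.5.2.1 also delays a Grade 3 drug-related case. Below Grade 3 it delays only through the investigator-judgment item.

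**Other routes to a stop in the body of the protocol**

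- A delay of more than 42 days from the last dose ends treatment. The exceptions are prolonged steroid tapers for drug-related events and approved delays for non-drug-related reasons. Any restart after such a delay needs Medical Monitor consultation (Section 4.5.3.1).
- The investigator may judge the risk substantial (Section 4.5.3.1) or continued participation against the subject's best interest (Section 3.5).
- A Grade 3 case recorded as a hypersensitivity reaction would stop under "Grade 3 drug-related uveitis, pneumonitis, bronchospasm, neurologic toxicity, myocarditis, hypersensitivity reaction, or infusion reaction of any duration require discontinuation".

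None of these reproduces the appendix rule, which turns on the diagnosis alone.

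**How the protocol handles similar stops.** Adrenal insufficiency is the closest comparator: its mandatory discontinuation is written into both the resume criteria of Section 4.5.2.1 and the stop list of Section 4.5.3.1. Section 4.5.2.1 also requires Medical Monitor involvement before resuming after persistent Grade 1 pneumonitis or a controlled endocrinopathy. It asks for none after a Grade 3 skin event.

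**Counts**

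- Upper bound on exposed subjects: 560 planned, randomized 1:1, so 560 / 2 = 280 in Arm A.
- Scheduled restart points inside the delay limit: 42 days / 14-day cycle = 3 dosing points after the last dose (Days 14, 28 and 42). If the Day 14 dose is the one missed, 3 − 1 = 2 remain (Days 28 and 42), neither needing Medical Monitor consultation after a skin event.

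**The case against.** The strongest reply is that the rule is already in the protocol. Section 4.5.1.1 names skin among the algorithm groups and sends investigators to Appendix 1. Section 4.5.1 does not say that Sections 4.5.2 and 4.5.3 are the only source of criteria. The resume rule is a permission, so a general permission and a specific prohibition can be read together, and an investigator can comply with both. Re-dosing would require overlooking the appendix and also judging that a patient with diagnosed SJS or TEN faced no substantial risk. A case meeting the serious adverse event definition would reach the sponsor within 24 hours under Section 6.1.1.

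Much of this is fair, and it makes an actual re-dosing unlikely. It does not remove the conflict. The restart sentence is directive once the resume criteria are met, the appendix is labelled guidance, no precedence is stated, and reporting an event does not bar a restart.

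Three narrower objections stand as limits. First, the conflict exists only if diagnosed SJS/TEN can be graded below 4. Grading is by CTCAE version 4, which the documents do not reproduce. Second, the skin flowchart is not shown, so the box to which the footnote attaches is unknown; that the rule applies at every grade is inferred from wording that states none. Third, the named Grade 3 stops in Section 4.5.3.1 are weak comparators, because they sit under the non-skin rule and some are broad categories. The argument does not need them. The suspected-case line in the fix is also the least necessary part, since it changes only what happens below Grade 3.

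**Conclusion.** The concern holds. For a drug-related, diagnosed SJS or TEN case graded below 4, the appendix and the dosing sections give different instructions. At Grade 3, with resolution inside the permitted delay, the body of the protocol directs a restart that the appendix forbids.

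The affected group is a subset of at most 280 subjects and may be zero; no frequency can be claimed from the documents. The conclusion assumes that SJS/TEN can be graded below 4 and that the unseen flowchart does not restrict the footnote. It is a patient-safety inconsistency of probably low frequency that should be corrected because correction is nearly free. It has no bearing on power, type I error or the overall survival comparison.

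**What to change.** Amend the two nivolumab sections:

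1. Section 4.5.3.1, permanent discontinuation: add diagnosed SJS or TEN regardless of grade, with a reference to Appendix 1. Confirm against the full skin flowchart that no grade limit was intended.
2. Section 4.5.2.1, delay list: add suspected SJS/TEN.
3. Section 4.5.2.1, resume criteria: state that subjects with diagnosed SJS or TEN may not resume nivolumab, in the way already done there for adrenal insufficiency.

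The cost is three short lines in a protocol amendment. Appendix 1, data collection, sample size and the analyses stay as they are.
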